Vital Signs ¹³	X	X		X	X
12-lead ECG ¹⁴	X	If clinically indicated and/or per local requirements		X	X

Table continued on next page

VISIT	Screening ¹	Study Treatment Period (Each Cycle = 14 Days)		Follow-up	
		Cycles 1 to 12²		Study Treatment Discontinuation Visit ³	30-Day Safety Follow-up Visit ⁴
Day		1	2 to 14	≤ 7 days from date of last dose or investigator decision to discontinue dose	30 days from date of last dose
Visit Window (business days)	-45 to -1	+5*	(no visit)	0	+7
Image Assessment ¹⁵	X	Every 6 weeks (+ 7 days) counting from C1D1 for the first 24 weeks, and then every 12 weeks (± 7 days) until subject develops radiographic disease by RECIST v1.1 or starts other systemic anticancer therapy			
Clinical Safety Labs ¹⁶	X	X		X	X
Thyroid Function Test (TSH, T4) ¹⁷		X	If clinically indicated	X	
Coagulation Parameters (PT, PTT and INR) ¹⁸	X	If clinically indicated		X	
Pharmacokinetics of ASP1650 (Serum)		See Table 2 below for sample collection schedule			
Antidrug Antibodies (ADA) for Immunogenicity		See Table 2 below for sample collection schedule			
Exploratory Biomarkers (Serum) ¹⁹		X		X	
Exploratory Biomarkers (Plasma) ¹⁹		X		X	
Tumor Markers (AFP, βhCG) ²⁰	X	X			
Whole Blood Sample for PGx (optional) ²¹		X			
Post-progression Tumor Sample (optional) ²²				X	
Concomitant Medication	X	X		X	X
AE²³	X	X		X	X

ADA: antidrug antibody; AE: adverse event; AFP: alpha-fetoprotein; βhCG: beta human chorionic gonadotropin; C: cycle; CT: computerized tomography; D: day; ECG: electrocardiogram; ECOG: European Cooperative Oncology Group; FFPE: formalin fixed paraffin embedded; ICF: informed consent form; INR: international normalized ratio; IRC: independent review committee; IRR: infusion-related reaction; IRT: interactive response technology; MRI: magnetic resonance imaging; PGx: pharmacogenomics; PT: prothrombin time; PTT: partial thromboplastin time; Q2W: every 2 weeks; RECIST: Response Evaluation Criteria In Solid Tumors; SAE: serious adverse event; T4: thyroxine; TSH: thyroid stimulating hormone

Footnotes continued on next page

*+5 day visit window does not apply to C1D1.

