1. **Screening:** The Screening period is 45 days. Re-screening may be allowed upon discussion with the medical monitor. Central laboratory results should be used to confirm eligibility, however if repeat screening labs are required, local laboratory results can be used to confirm eligibility. The screening labs used to determine eligibility should be collected within 14 days prior to C1D1. In situations where laboratory results are outside of the permitted range, the investigator may opt to retest the subject and subsequent within range central lab screening results may be used to confirm eligibility. In case of multiple central laboratory data within the Screening period, the most recent data should be used to confirm eligibility. Subjects requiring transfusions to meet eligibility criteria are not eligible. Radiologic imaging used to confirm eligibility must be conducted within 28 days prior to C1D1.
2. All subjects will be treated for a maximum of 12 cycles or until the subject meets study treatment discontinuation criteria.
3. **Study Treatment Discontinuation Visit (End of Study Treatment):** The Study Treatment Discontinuation Visit will take place ≤ 7 days following the last dose or the decision by the investigator to discontinue study treatment.
4. **30-Day Safety Follow-up Visit:** A 30-Day Safety Follow-up Visit should occur 30 days (+7 days) after the last dose of ASP1650 and will include the assessments as shown in the Schedule of Assessments above.
5. Subject must have an available tumor specimen in a tissue block or unstained serial slides, or subject is an appropriate candidate for tumor biopsy and is amenable to undergoing a tumor biopsy during the screening period. If a biopsy is performed, collection from a site other than lymph nodes is preferred. A minimum of 1 FFPE tumor tissue block with adequate viable tumor cells (preferred) OR a minimum of 9 FFPE unstained slides are required. If ≥ 9 slides cannot be provided, the sponsor should be contacted for further guidance.
6. For subjects who signed an optional ICF, an optional on-treatment tumor specimen collected ± 7 days of the C4D1 visit may be provided. A minimum of 1 FFPE tumor tissue block with adequate viable tumor cells (preferred) OR a minimum of 9 FFPE unstained slides are required. In cases where a pretreatment biopsy was performed, collection of the on-treatment specimen from the same site is preferred.

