12. Physical Exam: should include height (at Screening only), weight and ECOG performance status. All assessments should be taken predose on dosing days. A full physical exam is required at Screening. The physical exam only needs to be repeated on C1D1 if clinically significant changes from Screening are observed (in the opinion of the investigator). Targeted (symptom driven) physical exams should be conducted Q2W on day 1 of each cycle.
13. Vital signs (pulse, blood pressure, temperature) should be taken during every visit at the following time points:
 - Pre-dose at every visit
 - C1D1 and C2D1: Every 15 (\pm 5) minutes during ASP1650 infusion
 - Subsequent ASP1650 infusions: every 30 (\pm 10) minutes during ASP1650 infusions if the subject did not develop any AEs during the Post-infusion Observation Period of cycles 1 and 2. If subject develops AEs during C1D1, C2D1 or subsequent ASP1650 infusions, then collect every 15 (\pm 5) minutes during ASP1650 infusion
 - At 30 (\pm 10), 60 (\pm 10) and 120 (\pm 10) minutes post ASP1650 infusion during the Post-infusion Observation Period (for 1 or 2 hours; see footnote 10) 120 minute collection to be done only when observation period is 2 hours.
 - Unscheduled if clinically indicated
14. ECGs: a single ECG will be performed at Screening, the Study Treatment Discontinuation Visit, the 30-Day Follow-up Visit, and if clinically indicated or per local requirements. ECGs will be locally read. When collected on the same day, ECG should be collected prior to pharmacokinetic samples.
15. Imaging Assessments: Radiologic imaging will be evaluated at Screening (must be conducted within 28 days prior to C1D1) and every 6 weeks (+ 7 days) counting from C1D1 for the first 24 weeks and then every 12 weeks (\pm 7 days) thereafter until subject develops radiological disease progression per RECIST v1.1 by local investigator assessment or starts other systemic anticancer treatment, whichever comes earlier. Imaging will include CT scans with contrast of the thorax, abdomen, and pelvis. If CT scan with contrast is medically not feasible, MRI or CT scan without contrast may be used for imaging. Bone scans (or focal X-ray) or brain imaging should be performed if metastatic disease in bone or brain is suspected, respectively. The same mode of imaging should be utilized throughout the study unless medical necessity requires a change.

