7 STATISTICAL METHODOLOGY

A Statistical Analysis Plan (SAP) will be written to provide details of the analysis, along with specifications for tables, listings and figures to be produced. The SAP will be finalized before the database hard lock. Any changes from the analyses planned in SAP will be justified in the Clinical Study Report (CSR).

Prior to database lock, a Final Review of Data and TLFs Meeting will be held to allow a review of the clinical study data and to verify the data that will be used for analysis set classification. If required, consequences for the statistical analysis will be discussed and documented. A meeting to determine analysis set classifications may also be held prior to database lock.

In general, continuous data will be summarized with descriptive statistics (number of subjects, mean, standard deviation, minimum, median and maximum), and frequency and percentage for categorical data. Kaplan-Meier estimates will be provided for time-to-event endpoints. Separate data displays will be provided for the Safety Lead-in phase and phase 2 of the study unless specified otherwise.

Baseline will be defined as the last observation prior to first dose, unless otherwise specified.

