7.5.4 Vital Signs

Descriptive statistics will be used to summarize vital sign results and changes from baseline for subjects in the SAF by cohort, dose level and time point.

Potentially clinically significant vital signs will be defined and tabulated as described in the SAP. Vital signs data will be displayed in listings.

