6.5.4 Vital Signs

Descriptive statistics will be used to summarize vital sign results and changes from pre-dose on the day of infusion for subjects in the SAF by dose level and time point. Weight and BSA

results and change from baseline will also be summarized with descriptive statistics and listed.

Potentially clinically significant vital signs will be tabulated with summary statistics. The following potentially significant clinically significant criteria are defined for each parameter:

Vital Sign Variable	Criteria
SBP	≥ 180 mmHg AND ≥ 20 mmHg change from baseline
SBP	≤ 80 mmHg
DBP	≥ 105 mmHg AND ≥ 15 mmHg change from baseline
Pulse Rate	≥ 120 bpm AND ≥ 15 bpm change from baseline

Vital signs data will be displayed in listings.

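### SAP 6.5.4 takes vital-sign change from each infusion day's pre-dose value, so the protocol's within-subject change from baseline is not specified after cycle 1

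*SAP*

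**What the plan says.** The two documents name different reference values for the same summary.

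- **Protocol 7.5.4** plans to "summarize vital sign results and changes from baseline for subjects in the SAF by cohort, dose level and time point".
- **Protocol section 7** fixes the reference: "Baseline will be defined as the last observation prior to first dose, unless otherwise specified". Section 7.5.4 specifies nothing different for vital signs.
- **SAP 6.5.4** has: "Descriptive statistics will be used to summarize vital sign results and changes from pre-dose on the day of infusion". The summary is by dose level and time point.
- **The rest of SAP 6.5.4** keeps baseline as the reference for weight, BSA and three of the four criteria for potentially clinically significant values. The fourth criterion, low systolic pressure, is an absolute threshold.
- **SAP 6.5.3** gives an operational definition of baseline (last measurement before initial study drug), but only in the laboratory section.

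On data collection, Protocol Table 1, footnote 13 requires readings "Pre-dose at every visit", at intervals during the infusion and again afterwards. The Schedule of Assessments also marks vital signs at the Study Treatment Discontinuation Visit and the 30-Day Safety Follow-up Visit.

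**The concern.** Vital signs are part of a named secondary safety endpoint (Protocol 2.3.2), and the protocol says how their change is to be measured. The SAP describes a different quantity. Change from the same day's pre-dose value isolates what happens around one infusion. Change from study baseline also contains whatever has shifted between the first dose and that day. Using the first in place of the second removes the between-cycle part from the change summary and leaves no change value at visits without an infusion.

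This matters because subjects leave treatment over time, for progression, toxicity and other reasons (Protocol 6.1). Means at later cycles come from fewer and different subjects than the mean at baseline. A within-subject change compares each remaining subject with himself, which the results by time point do not do. Protocol 5.4.1 also asks investigators to judge vital-sign changes against the pretreatment value, so the study-baseline comparison is the one used elsewhere in the plan.

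**Working it through.** The documents give no figure to reproduce here. The check sets the two definitions side by side and applies them to the visit schedule.

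**Inputs**
- Reference values: SAP 6.5.4; Protocol 7.5.4 with section 7.
- Maximum number of infusion days: 12 (Protocol 5.1.1).
- Vital-sign time points: Protocol Table 1 and footnote 13.
- Discontinuation visit: "will take place ≤ 7 days following the last dose" or the decision to stop (Table 1, footnote 3).
- Follow-up visit: 30 (+7) days after the last dose (Table 1, footnote 4).

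**Definitions.** Let X(k, t) be the reading in cycle k at time t, and let B be the last reading before first dose.
- SAP change = X(k, t) − X(k, pre-dose)
- Protocol change = X(k, t) − B
- Hence Protocol change = SAP change + [X(k, pre-dose) − B]

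The bracket is the between-cycle shift, and it is what the SAP definition leaves out.

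**Applied to the schedule**

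| Reading | SAP change | Protocol change |
|---|---|---|
| Cycle 1, during and after infusion | Defined; normally equals the protocol change, because B is normally the C1D1 pre-dose value | Defined |
| Pre-dose, cycles 2 to 12 (12 − 1 = 11 readings at most) | 0 by construction | Defined |
| During and after infusion, cycles 2 to 12 | Defined, without the between-cycle shift | Defined |
| Discontinuation visit | Ordinarily not computable: no infusion is scheduled | Defined |
| 30-day visit | Not computable: no infusion that day | Defined |

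Eleven is a ceiling, reached only by subjects who receive all 12 cycles. The discontinuation window could in a rare case include an infusion day. The 30-day window cannot.

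**Illustration (all values assumed; the documents give none).** Take systolic pressure of 120 mmHg at baseline, a steady pre-dose drift of d mmHg per cycle, and a 3 mmHg rise during each infusion. At cycle 12 there have been 11 steps of drift.

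| d | Pre-dose change, SAP | Pre-dose change, protocol (11d) | Post-infusion change, SAP | Post-infusion change, protocol (11d + 3) |
|---|---|---|---|---|
| 0 | 0 | 0 | 3 | 3 |
| 1 | 0 | 11 | 3 | 14 |
| 2 | 0 | 22 | 3 | 25 |
| 4 | 0 | 44 | 3 | 47 |

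The SAP columns are the same whatever the drift. In the last row the post-infusion reading is 120 + 44 + 3 = 167 mmHg. That is below the 180 mmHg that the systolic criterion also requires, so a rise of 47 mmHg would not be flagged.

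**The case against.** The case on the other side is substantial, and most of it stands as a limit on the point.

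- **Results are summarised as well as changes.** The same SAP sentence covers the vital-sign values themselves by time point, and all data are listed. A reader might infer that drift across cycles or the end-of-treatment picture would be invisible. The documents do not support that: drift would appear in the results summary. Only the within-subject change statistic is lost.
- **Large shifts have other routes.** Three of the four significance criteria use change from baseline, and Protocol 5.4.1 has clinically significant changes recorded as adverse events. Shifts below the thresholds that the investigator does not judge significant would still pass both routes.
- **A same-day reference is sensible for acute effects.** Infusion-related reactions are the adverse event of special interest (Protocol 5.5.8), and readings are dense around the infusion. Using two references in one section is not in itself an error, and a zero in a reference row is normal. The difficulty is that the same-day reference takes the place of the protocol's summary when it could sit beside it.
- **The wording might mean the C1D1 pre-dose value.** That would agree with the protocol, but the sentence does not refer to the first infusion, and the plain reading is the day of each infusion.
- **Silence in the revision table.** A reader might infer an unrecorded switch because SAP section 7 does not mention vital signs. That does not follow: the table logs changes between SAP versions, not departures from the protocol, and the wording may date from version 1.0.
- **Table specifications.** SAP 6.1 leaves table formats to separate TLF specifications, which are not among the documents. It can be said that the SAP text does not specify the protocol's summary, not that it will never be produced.

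**Conclusion.** The point holds in a limited form. SAP 6.5.4 and Protocol 7.5.4 use different references for the descriptive vital-sign change. Under the SAP's wording the change is zero by construction at up to 11 pre-dose readings per subject, lacks the between-cycle shift at the other readings from cycle 2 on, and is unavailable at the 30-day visit and ordinarily at the discontinuation visit. What is missing is the within-subject change from baseline after cycle 1.

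This rests on the plain reading of the SAP sentence and on the visit schedule. The size of any understatement in mmHg depends on drift, for which the documents give no figure. The matter is minor: the output is descriptive, and response rate, the futility rule, DLT assessment, dose selection and error rates are unaffected. It is worth correcting because the protocol specifies the summary and the data will be there.

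**What to change.** In SAP 6.5.4:

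1. Summarise change from study baseline, defined as the last value before first dose, at all post-baseline time points, including the discontinuation and 30-day visits.
2. Keep change from same-day pre-dose as an additional summary for readings during and after infusion.
3. State that the significance criteria use study baseline.

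If the same-day reference was meant to replace the protocol's, the SAP should say so and give the reason. If the C1D1 pre-dose value was meant, naming it settles the matter.

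The cost is one sentence and one extra table. No new data, visits or protocol procedures are needed.

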6.5.5 Electrocardiograms

The 12-lead ECG results will be summarized by dose level and time point. A shift analysis table showing shifts from baseline in overall ECG (normal and abnormal) will be provided.

6.5.6 Eastern Cooperative Oncology Group Performance Status

Summary statistics (number and percent of subjects) for each category of the ECOG performance status at each assessment will be provided. The change from baseline to final visit or early termination will also be summarized. Negative change scores indicate an improvement. Positive scores indicate a decline in performance.

6.5.7 Immunogenicity

Immunogenicity of ASP1650 will be summarized for each dose level and scheduled time point using the frequency of antidrug antibody (ADA) positive subjects. The potential relationship between ASP1650 immunogenicity and ASP1650 pharmacokinetics, efficacy and safety profiles in subjects may be assessed.

6.6 Analysis of Pharmacokinetics

Descriptive statistics will include the number of subjects (n), mean, standard deviation, coefficient of variation (CV), geometric mean, geometric CV, median, minimum, maximum.

6.6.1 Serum Concentrations

Serum concentrations of ASP1650 will be listed and summarized using descriptive statistics by dose and scheduled time point. Standard graphics including mean serum concentration-time profiles and overlay (spaghetti) plots will be produced. Steady state of ASP1650 will be

evaluated using a visual inspection of individual participant trough concentrations versus visit overlaid with a mean profile.

6.6.2 Estimation of Pharmacokinetic Parameters

Noncompartmental (NCA) analysis will be performed to calculate ASP1650 pharmacokinetic parameters using Phoenix® WinNonlin® version 6.4 or higher (Certara USA, Inc., Princeton, NJ). Descriptive statistics will be provided for the NCA-based parameters whenever applicable.

PK parameters will be listed and summarized by dose level and visit. The following parameters will be summarized:

- AUC₃₃₆, C_{max}, t_{max}, C_{trough}
- Additional PK parameters as applicable: AUC_{inf}, AUC_{inf} [%extrap], AUC_{last}, t_{1/2}, t_{last}, CL, V_z

6.7 Analysis of Biomarkers

Additional post hoc statistical analyses may be outlined in a biomarker SAP.

Results of microscopic examination of CLDN6 will be summarized and listed for subjects with available results.

6.8 Other Analysis

Due to COVID-19, the assessments of some subjects may be affected. All visit-based and non-visit-based assessments affected by the COVID-19 pandemic will be listed.

6.9 Subgroup Analysis for Primary Efficacy Endpoint

The following subgroups may be explored:

- Tumor type: Seminoma vs non-seminoma or relapsed primary mediastinal non-seminomatous germ cell tumor vs mixed
- Prior lines of medication therapy: 2 vs ≥ 3
- Primary testicular site vs other (mediastinal or retroperitoneum)
- Presence of visceral metastases: yes vs no
- Late relapse: yes vs no
- Prior high-dose chemotherapy: yes vs no

6.10 Interim Analysis (and Early Discontinuation of the Clinical Study)

No formal interim analysis is planned during the Safety Lead-in phase. Safety, pharmacokinetic and other clinical data will be reviewed on an ongoing basis.

A futility analysis will be conducted 24 weeks after the first dose of the 13th subjects are enrolled in stage I of phase 2 of the study. The study may be stopped if we observed less than 2 confirmed response (confirmed CR or confirmed PR by modified RECIST 1.1) are observed 24 weeks after the first dose of the 13th subject.

6.11 Additional Conventions

6.11.1 Missing Data

Every effort will be made to resolve missing or incomplete dates for adverse events, concomitant medications, anti-cancer therapy, and death. If a partial date cannot be resolved, the most conservative imputation methods will be used to complete the missing information.

Missing or partial start and stop dates of adverse events and concomitant medication will be imputed using the following algorithm:

- Imputation rules for partial or missing stop dates:
 - If the month and year are present, then impute as the last day of that month.
 - If only the year is present, impute as December 31 of that year.
 - If the stop date is entirely missing, assume the event or medication is ongoing.

Imputation rules for partial or missing start dates:

Start Date		Stop Date				Partial: yyyy		Missing
		Complete: yyyymmdd		Partial: yyyymm		< 1 st dose	≥ 1 st dose	
		< 1 st dose	≥ 1 st dose	< 1 st dose yyyymm	≥ 1 st dose yyyymm	< 1 st dose yyyy	≥ 1 st dose yyyy	
Partial: yyyymm	= 1 st dose yyyymm	2	1	2	1	n/a	1	1
	≠ 1 st dose yyyymm		2		2	2	2	2
Partial: yyyy	= 1 st dose yyyy	3	1	3	1	n/a	1	1
	≠ 1 st dose yyyy		3		3	3	3	3
Missing		4	1	4	1	4	1	1

1 = Impute as the date of first dose; 2 = Impute as the first of the month; 3 = Impute as January 1 of the year; 4 = Impute as January 1 of the stop year

The imputed dates will be used to determine whether an AE is/is not treatment emergent. Listings of AEs and concomitant medications will present the actual partial dates; imputed dates will not be shown.

For secondary endpoint PFS or DOR, missing or incomplete death date will be imputed as the earliest feasible date on or after the date last known to be alive as the examples shown in the table below.

Incomplete Date of Death (YYYY MMM DD)	Date Last Know to be Alive (YYYY MMM DD)	Imputed Date of Death (YYYY MMM DD)
2005 APR ??	2005 MAR 31	2005 APR 01
2005 ??? 13	2005 MAR 31	2005 APR 13
2005 ??? ??	2005 MAR 31	2005 MAR 31
???? APR ??	2005 MAR 31	2005 APR 01
???? APR 13	2005 MAR 31	2005 APR 13
???? ??? ??	2005 MAR 31	2005 MAR 31

6.11.2 Outliers

All values will be included in the analyses.

7 REVISION AND RATIONALE

Version	Date	Changes	Comment/rationale for change
1.0	02Nov2018	started	
2.0	10Feb2021	updated	clarified blood draw schedule for post treatment period; allowed cohort 2 and beyond to have up to 4 subjects derivation of PFS inaccurately had noted registration date as first date; clarified to be first dose date Updated to align with protocol version 3.1 incorporating Nonsubstantial Amendment 1 Updated to describe biomarker analysis

